6.2.4. Analysis of Covariance (Repeated Measures)

Analyses of the clinical laboratory values will also be carried out using a restricted maximum likelihood (REML) based repeated measures linear mixed model (MMRM) to evaluate the effect over time by providing LS mean estimates, 95% CIs of change and percentage change from Baseline at each DB post-Baseline visit. Model covariates include then randomization stratification values (ie, UDCA use [yes, no] and pre-randomization total bilirubin [$\leq 1.5 \times \text{ULN}$, $> 1.5 \times \text{ULN} - < 2.5 \times \text{ULN}$]), Baseline of the parameter being estimated, and a treatment by visit interaction term. An unstructured (5×5) covariance model will be used. If the computational algorithm fails to converge, the following structures will be executed: heterogeneous Toeplitz, Toeplitz, heterogeneous First-Order Autoregressive [AR (1)], heterogeneous compound symmetry (HCS), and compound symmetry (CS). The covariance structure converging to the best fit, as determined by Akaike's information criterion (AIC), will be used. The Kenward and Roger method will be used to calculate the denominator degrees of freedom for the test of fixed effects.

Example SAS® code for the ANCOVA with repeated measures is as follows:

```
ODS graphics on;  
proc mixed data=ADLB noclprint plots=residualpanel;  
  class subjid week ucdafl tbilfl trt;  
  model change=week Baseline ucdafl tbilfl trt trt*week/ ddfm=kr;  
  repeated week / subject=subjid type=uns;  
  lsmeans trt trt*week / cl diff alpha=0.05;  
  title1 "Linear Mixed Effects Model Based Estimates of XXXX Means by Visit";  
  title2 " Fixed Effects for Visit, Randomization Strata and Baseline as Covariates, and  
  Treatment by Visit Interaction";  
run;  
ODS graphics off;  
quit;
```

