**Table 1: Schedule of Trial Procedures: Double-Blind Phase (Continued)**

Visit Type a	Screening (Day -30 to Day -1)	Day 0 b	Visit W2	Visit W6	Visit W12 c	Visit W14	Visit W18	Visit W24 d / LTSE D1/ EOT e	FU (4 wks) f
Visit Windowg	≤30d		±3d	±1wk	±1wk	±1wk	±1wk	±1wk	±1wk
Dispense Investigational Product		X q			X			X r	
Investigational Product Accountability/ Compliance s			X	X	X	X	X	X	
Laboratory Evaluationst									
Serum Chemistry, Hematology, & Coagulation Parameters	X u	X	X	X	X	X	X	X	X
FGF-19		X			X			X	
CRP		X			X			X	
ELF Markers & Other Analytes v		X			X			X	
Plasma Bile Acids		X			X			X	
C4		X			X			X	
PK w					X			X	
Apolipoprotein & NMR Lipoprotein Panel		X			X			X	
Dipstick Urinalysis	X	X			X			X	
Urine Pregnancy Test x	X	X			X			X	X
Fecal Sample y		X			X			X	
Genetics Study z		X						X	

- a Subjects must be fasted prior to all clinic visits (except Screening) and investigational product should not be administered prior to clinic visits (see [Section 8.1](#)).
- b Day 0 must occur by Day 31 for a subject to be eligible to continue in the trial.
- c Week 12 is the Dose Titration visit.
- d The Week 24 visit is the final visit during the DB treatment period. For subjects who continue into the LTSE, the Week 24 visit is also Day 1 of the LTSE, and unblinding occurs after the Week 24/LTSE Day 1 procedures have been completed (except dispensing of open-label investigational product).
- e End of treatment (EOT) visit is completed for any randomized subject who discontinues the study prior to reaching Week 24 of the DB phase; this should occur as close as possible to the final dose of investigational product. If a subject discontinues on the day of a scheduled trial visit, the procedures from the scheduled visit will be recorded as EOT in the CRF.
- f Follow-Up visit: If a subject discontinues the study prior to the end of Week 24 or does not proceed into the LTSE, he/she returns to the site for a Follow-Up visit, which should occur 4 weeks ( $\pm 1$  week) after her/his last dose of investigational product.
- g Timing of all visits is relative to Day 0.
- h Height is measured at the Screening visit only.

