3. STUDY DESIGN AND PLAN

This is a Phase 2, randomized, double-blind, placebo-controlled, dose-finding evaluation of the efficacy and safety of OCA in subjects with PSC. The trial design is shown in [Figure 1](#). Approximately 75 subjects who provide written informed consent and meet all of the inclusion

and none of the exclusion criteria will be randomized to 1 of 3 treatment groups as follows: 1.5 mg titrating to 3 mg OCA, 5 mg titrating to 10 mg OCA, or placebo in a 1:1:1 ratio. Subjects will administer investigational product orally, once daily for 2 consecutive 12-week periods. Randomization will be stratified by the presence or absence of concomitant UDCA use and total bilirubin level ($\leq 1.5 \times \text{ULN}$ or $> 1.5 \times \text{ULN}$ but $< 2.5 \times \text{ULN}$). No more than 50% of subjects randomized will be administering UDCA at the time of randomization.

[figure not shown]
For the first 12 weeks after randomization, the subject's dose will be 1.5 mg OCA, 5 mg OCA, or placebo. After 12 weeks, the subject's dose will be titrated – 1.5 mg OCA titrating to 3 mg OCA and 5 mg OCA titrating to 10 mg OCA – and DB treatment will continue for a further 12 weeks at that dose.

Subjects will have a screening period of up to 30 days prior to Randomization/Day 0. Subjects will attend on site clinic visits at Weeks 2, 6, 12, 14, 18, and 24. The final visit during the DB phase will occur at Week 24, after which subjects will be asked to reconfirm their consent for participation in the LTSE phase (a further 24 months).

Upon a subject's completion of the DB phase, the trial blind will be broken in order to assign the starting OCA dose for the LTSE phase. It is intended that subjects will commence treatment at 5 mg OCA, except those subjects who completed treatment in the DB phase with 10 mg OCA who will continue at 10 mg OCA unless safety and tolerability warrant a dose reduction to 5 mg. The titration schedule and options for the LTSE phase are detailed in the protocol.

The overall study duration is up to 32 months, including up to a 30-day Screening period, 6 month DB period, followed by a 24-month open-label LTSE period, and a 1-month follow-up period. The LTSE may be extended as determined by the sponsor via protocol amendment and regulatory and Institutional Review Board/Independent Ethics Committee review and approval.

Figure 1: Study Design Schematic

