9.1. Primary Efficacy Analyses

The primary efficacy endpoint is the Week 24 change from Baseline in ALP. Using the ITT population, the primary efficacy analysis will compare the Week 24 change from Baseline in ALP between OCA 10 mg treatment group and placebo and OCA 3 mg treatment group and placebo using an ANCOVA model with treatment group, visit, and randomization strata as fixed effects, and Baseline ALP as a covariate.

In order, to provide estimates of the change from Baseline and corresponding 95% CI, the repeated measures ANCOVA methods described in [Section 6.2.3](#) will be applied. Model fit will be assessed in order to determine the validity of the estimates. The analysis will be repeated with percentage change from Baseline as the dependent variable. Estimates of least-square (LS) means, SEs, and 95% CIs will be presented by treatment group.

The values, change from Baseline, and percentage change from Baseline will be summarized using observed values by treatment group and visit using arithmetic summary statistics as described in [Section 6.2.1](#).

A hierarchical approach will be used for multiplicity adjustment across the primary efficacy endpoint for other visits and doses as described below. If the primary efficacy analysis is statistically significant ($p < 0.05$), the following order will be used in the testing procedure to compare the change from Baseline in ALP between OCA and placebo:

- Week 12: OCA 5 mg treatment group (randomized to 5 mg for the initial 12 weeks followed by 10 mg for the latter 12 weeks) vs. placebo
- Week 24: OCA 3 mg treatment group (randomized to 1.5 mg for the initial 12 weeks followed by 3 mg for the latter 12 weeks) vs. placebo
- Week 12: OCA 1.5 mg treatment group (randomized to 1.5 mg for the initial 12 weeks followed by 3 mg for the latter 12 weeks) vs. placebo

If at any step a comparison above is not statistically significant, then all subsequent comparisons will be exploratory rather than confirmatory.

Sensitivity analysis for the primary efficacy analysis will be performed using the W12C and W24C Populations. In addition, the arithmetic summary statistics will be presented by antibiotic use, IBD, UC, and CD subgroups as described in [Section 6.2.8](#).

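### The SAP's repeated-measures model states a 5×5 covariance for six visits and holds the baseline slope constant across visits

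*SAP*

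**What the plan says.** SAP 6.2.4 describes a REML mixed model, run in addition to the ANCOVA of Section 6.2.3, that is to give least-squares means and "95% CIs of change and percentage change from Baseline at each DB post-Baseline visit". On the covariance it says: "An unstructured (5×5) covariance model will be used". It then lists simpler structures to try should that one fail ("covariance model will be used. If the computational algorithm fails to converge").

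The schedule is in SAP Section 3: "Subjects will attend on site clinic visits at Weeks 2, 6, 12, 14, 18, and 24". Protocol Table 1 marks the row "Serum Chemistry, Hematology, & Coagulation Parameters", which includes ALP, at all six of those visits. SAP 8.1 counts completion at Week 24 and at each of the other five, defining each by a non-missing ALP.

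The mean model in the example code is "model change=week Baseline ucdafl tbilfl trt trt*week/ ddfm=kr", and the covariance statement is "repeated week / subject=subjid type=uns". Baseline enters once. The only interaction with visit is treatment by visit, and the text of the section agrees with the code.

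SAP Appendix A lists the MMRM results as Tables 14.2.2.1 (ALP), 14.2.4.2 (hepatic biochemistry) and 14.2.5.2 (inflammation and disease markers). SAP 9.1 says that "the repeated measures ANCOVA methods described in" Section 6.2.3 will provide the estimates of change and their confidence intervals. Section 6.2.3 is the ANCOVA section, and its code has neither a visit term nor a REPEATED statement.

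**The concern.** A model that reports every double-blind visit cannot have an unstructured matrix with fewer rows than there are visits. The SAP does not say which visit would be left out, so the written specification and the analysis that gets run will differ. SAP Section 1 requires deviations from the plan to be documented in the study report, so even a harmless mismatch has to be explained later.

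The single baseline slope matters for a different reason. Change from baseline is usually only weakly related to baseline soon after the start and more strongly related later, as the correlation between the two ALP values falls. A common slope is then wrong for Week 24, the visit of most interest. With no dropout this costs precision only. If the subjects who leave differ in baseline between arms, the wrong slope no longer averages out and the Week 24 contrast is shifted. The SAP assumes 20% dropout and, outside the responder and LOCF analyses, does not impute, so the MMRM's mean model has to carry the adjustment.

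**Working it through.** **Dimension.** The inputs are the six visits in SAP Section 3 (Weeks 2, 6, 12, 14, 18, 24) and serum chemistry at all six in protocol Table 1. An unstructured matrix for k visits has k(k+1)/2 parameters.

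- Stated: k = 5, 5 × 6 / 2 = 15.
- Scheduled: k = 6, 6 × 7 / 2 = 21.
- Markers drawn only at Weeks 12 and 24 (CRP, ELF markers and other analytes in Table 1): k = 2, 2 × 3 / 2 = 3.

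No sampling schedule in the documents gives k = 5.

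**Cost of the extra term.** A separate baseline slope per visit replaces 1 slope by 6, so it uses 5 more degrees of freedom. The full data set has at most 75 × 6 = 450 observations.

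**Precision at Week 24, complete data.** Let b24 be the true slope of Week 24 change on baseline, b the fitted common slope, g = |b24 − b|, S the baseline SD and σ the residual SD at Week 24 with the correct slope. The adjusted contrast is the difference in mean change minus b times the difference in mean baseline. Ignoring the estimation of b, the ratio of its standard error to that with the correct slope is √(1 + g²S²/σ²).

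The documents give neither slopes nor correlations, so these are assumptions. Take equal SDs at baseline and Week 24 with correlation ρ, so that σ² = S²(1 − ρ²) and b24 = −(1 − ρ). The common slope is pulled toward the early, tightly correlated visits, so g is a large part of 1 − ρ.

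| Assumed ρ | Assumed g | g²/(1 − ρ²) | SE ratio |
|---|---|---|---|
| 0.9 | 0.05 | 0.0025/0.19 = 0.013 | 1.007 |
| 0.8 | 0.18 | 0.0324/0.36 = 0.090 | 1.044 |
| 0.6 | 0.30 | 0.09/0.64 = 0.141 | 1.068 |

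An illustrative simulation at 25 per arm, with assumed correlations and complete data, gave about 4%, which lies inside this range.

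**Bias at Week 24 under dropout.** If D is the difference between arms in mean baseline among subjects still observed at Week 24, the shift in the contrast is about g × D. This is approximate for the MMRM, because the earlier visits of those who left also inform the estimate.

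- With D = 55 U/L: g = 0.05 gives 2.75 U/L, g = 0.2 gives 11 U/L, g = 0.3 gives 16.5 U/L.
- With D = 0: no shift, whatever g is.

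The same simulation, with dropout that depended on baseline differently by arm, gave a bias of about 11 U/L, and the baseline-by-week term removed it. To see what that requires, suppose 20% leave an arm and their mean baseline is Δ above the arm mean. The mean of those who remain then falls by 0.2Δ/0.8 = 0.25Δ. If this happens in one arm only, D = 55 needs Δ = 220 U/L. If it happens in opposite directions in the two arms, it needs Δ = 110 U/L in each. That is marked selection.

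**The case against.** The best defence is that neither item changes a planned result. In the example code, week is a class variable and the repeated effect, and no visit is filtered out. The fitted matrix will therefore be as large as the number of weeks in the data, whatever the text says. The common slope is not a slip either: text and code agree on it, and it is a permissible, more parsimonious model. No data in the documents show that the slope changes with time. Most of this stands. It makes the first item a text correction and the second a recommendation rather than an error.

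Three stronger readings are tempting but not supported.

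- A reader might infer that 5×5 discards one visit, 75 of 450 observations or 17%. That would follow only if the dimension were enforced by dropping a visit. The section asks for estimates at every visit and names none to omit.
- A reader might infer that the covariance keyword in the code is invalid. The documents do not list valid keywords. The text says unstructured, and the code is offered as an example, so this is at most something for the programmer to check.
- A reader might infer that the faulty model produces the primary estimate, since SAP 9.1 uses the words repeated measures. But 9.1 cites 6.2.3, whose code is labelled as the primary analysis. Section 6.2.3 also excludes the treatment-by-visit term that 6.2.4 includes, and the MMRM for ALP has its own table.

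**Conclusion.** The concern holds as a minor point about the MMRM outputs. The stated dimension contradicts the SAP's own visit schedule and should read 6×6 for the laboratory values taken at all six visits. No data loss and no effect on a result are shown.

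The common baseline slope is a restrictive choice with a small expected cost: a standard error at Week 24 larger by a few percent. Bias arises only if dropout depends on baseline differently in the two arms. Its size rests entirely on assumed correlations and dropout, and the 11 U/L figure illustrates marked selection rather than forecasting it.

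Whether any of this touches the primary estimate cannot be settled from the documents. SAP 9.1 names repeated-measures methods and lists visit as a fixed effect, while the section that it cites has neither in its code. That conflict needs correcting in its own right. A model with visit but without treatment by visit would estimate a treatment effect averaged over visits, not the Week 24 effect that defines the endpoint.

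**What to change.** - In SAP 6.2.4, replace 5×5 with unstructured (6×6) and list Weeks 2, 6, 12, 14, 18 and 24. Add that markers sampled only at Weeks 12 and 24, which feed Table 14.2.5.2, have a 2×2 matrix, so that the new figure is not wrong for them.
- Add `Baseline*week` to the covariates in the text and to the MODEL statement. This costs 5 model degrees of freedom for six visits and 1 for two visits. If the common slope is kept, give the reason.
- In SAP 9.1, correct the cross-reference and wording so that one model is named as the source of the primary Week 24 estimate, with the MMRM labelled as supportive if that is its role.
- Have the programmer check the covariance keyword while editing the example code.

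These are a few lines of SAP text and code, to be made before database lock. Visits, data collection and sample size do not change.

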6.2.5. Median and Confidence Interval Estimation Methods

Hodges Lehmann estimation will be used to provide estimators of the median difference and 95% CIs for the median difference.

6.2.6. Geometric (Natural Log Transformed) Summaries

In order to calculate a geometric mean and corresponding 95% CI, the following steps are used:

- Transform the data by taking natural logarithms ($\ln = \log_e$)
- Calculate the mean and 95% CI of the \log_e -transformed data
- Exponentiate the mean and the lower and upper CIs back to the original scale in order to obtain the geometric mean and corresponding 95% CI.

The geometric coefficient of variation (geometric CV%) is calculated as $100 * \sqrt{e^{SD^{**2}} - 1}$ where SD is the SD of the \log_e -transformed data.

6.2.7. Multiple Comparisons/Multiplicity

A hierarchical approach will be used for multiplicity adjustments. If the primary efficacy analysis is statistically significant ($p < 0.05$), the following order will be used in the testing procedure to compare the change from Baseline in ALP between OCA and placebo:

- Week 12: OCA 5 mg treatment group (randomized to 5 mg for the initial 12 weeks followed by 10 mg for the latter 12 weeks) vs. placebo
- Week 24: OCA 3 mg treatment group (randomized to 1.5 mg for the initial 12 weeks followed by 3 mg for the latter 12 weeks) vs. placebo
- Week 12: OCA 1.5 mg treatment group (randomized to 1.5 mg for the initial 12 weeks followed by 3 mg for the latter 12 weeks) vs. placebo

If at any step the comparison is not statistically significant, then all subsequent comparisons will be exploratory rather than confirmatory.

Multiplicity adjustments will not be applied for any other statistical testing.

6.2.8. Subgroup Analyses

Subgroup analyses will be evaluated as deemed appropriate. Subgroups are defined as follows:

- Antibiotic use after first dose (Yes/No) – World Health Organization Anatomical Therapeutic Chemical (ATC) codes starting with 'J01' and the medication start date is on or after the first dose of investigational product; for analysis of the primary efficacy endpoint.
- Age (≤ 65 years, > 65 years),
- BMI ($< 30 \text{ kg/m}^2$ vs $\geq 30 \text{ kg/m}^2$)
- Baseline UDCA use (Yes vs No)
- Baseline Total Bilirubin ($\leq 1.5 \times \text{ULN}$ vs $> 1.5 \times \text{ULN}$)
- ethnicity (Hispanic or Latino, Not Hispanic or Latino, Not Reported, Unknown)

- race (American Indian or Alaska Native, Asian, Black or African American, Native Hawaiian or Other Pacific Islander, White)
- gender (Male, Female)
- IBD (Yes vs No)
- Crohn's disease (Yes vs No)
- Ulcerative colitis (Yes vs No)
- Median TE Score (< vs \geq Median score for all ITT subjects)

6.3. Data Handling

6.3.1. Baseline Values

Baseline values are defined as follows:

- **Efficacy, Clinical laboratory, and PD endpoints:** the mean of all available evaluations prior to first dose of investigational product.
- **Lipoprotein assessments:** the last non-missing fasted assessment prior to first dose of investigational product.
- **ECG assessment:** the last available non-missing assessment prior to first dose of investigational product.

For any other quantitative parameters, Baseline is defined as the mean of all available evaluations prior to administration of investigational product on Day 1.

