### **11.2.5. Laboratory Assessments**

All laboratory tests will be analyzed by a Central Laboratory (except urine or serum pregnancy tests). Blood and urine samples will be collected and analyzed or tested, according to the SOP of the testing facility and all samples will be collected while the subject is fasting. Full instructions concerning the number, volume, and type of samples to be collected at each visit will be detailed in the trial-specific laboratory manual. The manual will also include details of sample collection methods, labelling, and shipping information.

Fasting (8 hours) blood samples are required for lipid, glucose (serum chemistry), and bile acid analyses. For consistency, subjects will be instructed to attend each of their onsite visits (except Screening) in a fasted state and subjects should remain fasted until their blood samples have been collected. At each visit the Investigator or designee will verify whether the subject has fasted for at least 8 hours and record fasting status in the source and CRF. If the subject reports having

eaten (water is permitted) within 8 hours, this should be documented accordingly in the source and CRF and remind the subject that fasting is required prior to all trial visits.

- Hematology and Coagulation (hemoglobin, hematocrit, white blood cell [WBC] count with differential, platelets, red blood cell [RBC] count, INR, prothrombin time, partial thromboplastin time)
- Serum chemistry including albumin, blood urea nitrogen (BUN), creatinine, direct (conjugated) bilirubin, indirect (unconjugated) bilirubin, total bilirubin, AST, ALT, ALP, GGT, electrolytes [calcium, chloride, potassium, sodium, magnesium], glucose, total protein, and blood lipids (total cholesterol, low density lipoprotein [LDL], HDL and very low density lipoprotein (VLDL) fractions and triglycerides [TG])
- Apolipoprotein and NMR lipoprotein panel: ApoA1, ApoB, ApoE, HDL, LDL, triglycerides, VLDL. HDL, LDL, and VLDL cholesterol concentrations, particle numbers and sizes will be assessed.
- IgG4 (Screening visit only)
- Urine dipstick (pH, specific gravity, protein, glucose, ketones, bilirubin, blood)

All subjects with laboratory tests containing clinically significant abnormal values are to be followed regularly until the values return to normal ranges; until a valid reason, other than test-article related AE, is identified; or until further follow-up is deemed medically unnecessary.

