### **12.5.2. Clinical Laboratory Evaluations**

Planned laboratory assessments are listed in [Appendix A](#). All hematology, clinical chemistry, urinalysis, and fecal sampling results will be listed by treatment, subject, and visit, including scheduled and unscheduled/repeat measurements. Laboratory assessments that are outside of normal ranges will be flagged. Baseline values, the values at each visit, and changes from Baseline values will be summarized for each of the quantitative laboratory assessments by treatment group. Baseline is defined as the mean of all available evaluations prior to treatment (except for lipoprotein assessments where Baseline will be the fasted Day 0 assessment).

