10.4. Clinical Laboratory Evaluations

Clinical laboratory evaluations during the DB phase are assessed at the central laboratory. A listing of available laboratory reference/normal ranges for each laboratory parameter will be provided including age, sex, values with units. All analyses of lipoprotein will include fasted samples only.

Quantitative hematology, coagulation, serum chemistry, apolipoprotein and nuclear magnetic resonance (NMR) lipoprotein panel laboratory parameters will be summarized by treatment group in SI units using arithmetic summary statistics as described in [Section 6.2.1](#) at Baseline and at each scheduled DB post-Baseline visit. Change from Baseline will also be summarized in the same manner. Re-tests or unscheduled visit results after first dose of investigational product in the DB phase will not be summarized but will be included in the data listings.

In addition, shift tables (ie, low-normal-high at Baseline versus low-normal-high at DB post-Baseline Visit in a 3-by-3 contingency table) from Baseline to worst value, last value, and at each scheduled DB post-Baseline visit will be provided for hematology, coagulation, and serum chemistry by treatment group.

Urinalysis results will not be summarized but will be provided in a data listing.

Listings of all laboratory values will flag values outside of the normal range as high (H) or low (L) and indicate whether or not a value is clinically significant (CS), based on investigator judgment.

For laboratory test results that are below the quantifiable limits:

Imputed laboratory result = (numeric portion of the result) \times 0.9.

For laboratory test results that are above the quantifiable limits:

Imputed laboratory result = (numeric portion of the result) \times 1.1.

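### Baseline for serum-chemistry glucose averages a Screening sample that need not be fasted with the fasted Day 0 sample, and the SAP does not say which lipids escape that rule

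*SAP*

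**What the plan says.** **Fasting.** Protocol 11.2.5 states: "Fasting (8 hours) blood samples are required for lipid, glucose (serum chemistry), and bile acid analyses". It then says that "subjects will be instructed to attend each of their onsite visits (except Screening) in a fasted state", and footnote a of Table 1 repeats the Screening exemption. Earlier in 11.2.5, however, another sentence says that "all samples will be collected while the subject is fasting", which does not agree with the exemption.

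**Sampling.** Table 1 schedules serum chemistry at Screening, Day 0 and every later double-blind visit. The panel contains glucose, total cholesterol, LDL, HDL, VLDL and triglycerides (Protocol 11.2.5), and Appendix A adds free fatty acids. The apolipoprotein and NMR lipoprotein panel has one scheduled pre-dose draw, on Day 0.

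**Baseline.** For efficacy, clinical laboratory and PD endpoints, SAP 6.3.1 uses "the mean of all available evaluations prior to first dose of investigational product". For lipoprotein assessments it uses "the last non-missing fasted assessment prior to first dose of investigational product". Protocol 12.5.2 makes the same split: "except for lipoprotein assessments where Baseline will be the fasted Day 0 assessment".

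**Analysis.** SAP 10.4 summarizes serum chemistry by treatment group as values, change from Baseline and low/normal/high shifts. Its only fasting restriction is "All analyses of lipoprotein will include fasted samples only". Neither document lists which analytes count as lipoprotein.

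**The concern.** The sponsor already accepts that a Baseline for fasting-sensitive analytes should come from a fasted sample, and applies that to lipoproteins. Glucose stands beside lipids in the protocol's own fasting requirement but falls under the general averaging rule. Total cholesterol and triglycerides could be programmed either way.

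If fed values exceed fasted values, a partly fed Baseline is too high. A subject with no real change then appears to fall, a real rise looks smaller within the arm, and some subjects near the upper limit are classed as high at Baseline only because they had eaten. Those subjects cannot then appear as new elevations in a shift table.

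Safety is a primary objective. For serum chemistry as safety data, SAP Appendix A lists only visit summaries and shift analyses, which are the displays that Baseline feeds directly.

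A smaller gap of the same kind exists after Baseline. When a subject has eaten, sites record it and remind the subject, but nothing tells them to omit the sample, and SAP 10.4 filters only lipoprotein results.

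**Working it through.** The plan states no figure on this point, so there is nothing to reproduce. The check is algebra, followed by two simulations.

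**Inputs from the documents**
- One Screening and one Day 0 serum-chemistry draw before dosing (Protocol Table 1).
- A possible further Screening-period sample for ALP or bilirubin (Protocol 8.6.3). I assume it would add a glucose value if the whole panel is run.
- Screening precedes randomization, which is 1:1:1.

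**Assumed, because the documents do not give them**
- f, the share of subjects unfasted at Screening, from 0 to 1.
- d, the unfasted-minus-fasted difference, taken as positive.
- Day 0 and post-Baseline samples fasted.

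**Mean change.** With k Screening-period samples and one Day 0 sample:

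expected Baseline = fasted mean + [k/(k+1)]·f·d

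bias in within-arm change = -[k/(k+1)]·f·d

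| f | k = 1 | k = 2 |
|---|---|---|
| 0 | 0 | 0 |
| 0.25 | -0.125d | -0.167d |
| 0.5 | -0.25d | -0.333d |
| 0.75 | -0.375d | -0.5d |
| 1 | -0.5d | -0.667d |

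For illustration only, let d for glucose be 10 to 30 mg/dL. With k = 1 the spurious change is -5 to -15 mg/dL at f = 1 (0.5 × 1 × d) and -2.5 to -7.5 mg/dL at f = 0.5 (0.5 × 0.5 × d).

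**Contrast with placebo.** The same term applies in every arm in expectation, so it cancels. A simulation with 400,000 subjects per arm and a true OCA rise of 0.5d gave:

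| f | OCA change | Placebo change | Difference |
|---|---|---|---|
| 0 | 0.50d | 0.00d | 0.50d |
| 0.5 | 0.25d | -0.25d | 0.50d |
| 1 | 0.00d | -0.50d | 0.50d |

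With a fasted Day 0 Baseline, OCA returns to about 0.50d and placebo to about 0 at every f. The difference is about 0.50d under both rules.

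**Shift tables.** A category is a threshold on Baseline, so the shift does not simply cancel. Purely assumed values on an arbitrary scale: ULN 100, fasted mean 90, between-subject SD 8, within-subject SD 4, true OCA rise 8.

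- Share classed high at Baseline, fasted Day 0 rule: SD = √(64 + 16) = 8.94, z = (100 - 90)/8.94 = 1.12, giving 13%.
- Same share under the averaging rule with d = 10 and f = 1: mean 95, SD = √(64 + 8) = 8.49, z = (100 - 95)/8.49 = 0.59, giving 28%.

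Simulated OCA-minus-placebo difference in normal-to-high shifts, as a percentage of all subjects in the arm:

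| Baseline rule | d = 10 | d = 20 |
|---|---|---|
| Fasted Day 0 | 23 points | 23 points |
| Mean, f = 0.5 | 20 points | 15 points |
| Mean, f = 1 | 15 points | 5 points |

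These figures show the mechanism. They do not predict this trial.

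**The case against.** **Most lipids are already protected.** HDL, LDL and VLDL are lipoproteins, and SAP 6.3.1, SAP 10.4 and Protocol 12.5.2 all hold lipoproteins to fasted samples. Triglycerides are also a named component of the apolipoprotein and NMR lipoprotein panel. Because that panel has no scheduled Screening draw, a rule choosing the last fasted pre-dose value has practical effect mainly if it reaches the serum-chemistry lipids. This stands. A reader might infer that serum-chemistry lipids as a class have a mixed Baseline; the documents do not support that. For total cholesterol and triglycerides the fault is an undefined term, not a demonstrated wrong Baseline.

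**Screening is not stated to be unfasted.** The documents only lift the requirement, so some subjects may have fasted, and the effect shrinks in proportion to f. This also stands. The sentence saying all samples are taken fasting does not settle the matter, because 11.2.5 and Table 1 both exempt Screening explicitly. In addition, Protocol 8.6.3 gives the instruction to fast at Screening, for the next visit.

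**The placebo arm shows the same shift.** For mean change this is correct. A reader might infer that a real drug effect could be hidden altogether, but a true rise reported as zero on OCA would sit beside an equal fall on placebo. The defence does not extend to shift counts, where misclassified Baseline categories can reduce the difference between arms.

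**Free fatty acids are marginal.** They appear only in Appendix A, which notes that some tests may not be performed. The assumption that fed exceeds fasted may also fail for them, so the argument there is consistency, not direction.

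**Conclusion.** The point holds for glucose. Following the SAP as written gives it a Baseline that pools a sample not required to be fasted with a fasted one, contrary to the protocol's own requirement. Total cholesterol and triglycerides need clarifying, and free fatty acids have no fasted rule.

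The size is -0.5·f·d in within-arm mean change with one sample at each pre-dose visit, up to -0.667d with an extra unfasted Screening sample, plus misclassified Baseline categories in the shift tables. The downward direction requires d > 0. The magnitude rests entirely on f and d, which the documents do not give.

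A reader might also infer that the dyslipidaemia analysis is compromised. It is not: SAP 10.3.2 works from adverse event preferred terms and time to first onset, not change from Baseline. Glucose is neither an efficacy endpoint nor an event of special interest, and the listings flag out-of-range values whatever the Baseline. This is an inexpensive correction to safety displays, with no bearing on the primary ALP comparison.

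**What to change.** 1. In SAP 6.3.1, apply the existing rule, "the last non-missing fasted assessment prior to first dose of investigational product", to glucose, total cholesterol and triglycerides, and to free fatty acids if assayed. List every analyte meant by lipoprotein assessments, including serum-chemistry HDL, LDL and VLDL.
2. In SAP 10.4, apply the fasted-only restriction to the same list, using the fasting status recorded in the CRF. Leave the averaged Baseline in place for all other analytes.
3. In Protocol 11.2.5, reconcile the sentence that all samples are taken fasting with the Screening exemption.
4. Confirm that the CRF holds fasting status for Day 0. Protocol 11.2.5 requires it at each visit, but the Day 0 procedures in 8.6.4 do not repeat the check that appears from Week 2 onward.

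No new data are needed. For these analytes Baseline rests on one sample, so it is slightly less precise, and some unfasted post-Baseline values drop out of the summaries. A subject with no confirmed fasted pre-dose sample would have no Baseline for them. Unfasted values can stay in the listings.
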